## **Brentuximab vedotin (ADCETRIS®)**

### **Clinical Study Protocol C25003 Amendment 7, EudraCT: 2011-005450-60**

Patient-reported outcomes will be evaluated using the EORTC QLQ-C30, the FACIT-Dyspnea 10 questionnaire, the EQ-5D questionnaire, and the abbreviated Functional Assessment of Cancer Therapy—Neurotoxicity (FACT-Ntx; Abbreviated).

Relationships between plasma levels of brentuximab vedotin, soluble CD30, and CD30 expression on lymphoma cells will be assessed. A possible dose response for any such effects as well as the presence of ATAs may be subsequently examined.

Patients may discontinue therapy at any time. Patients will attend the EOT visit 30 ( $\pm 7$ ) days after completion of their last dose of frontline therapy.

#### **4.2 Number of Patients**

Approximately 1240 patients (approximately 620 patients per treatment arm) will be randomized in this study from approximately 250 study centers globally.

#### **4.3 Duration of Study**

Patients will be screened within 4 weeks of randomization, receive a maximum of six 28-day cycles of A +AVD or ABVD treatment (approximately 6 months), and will have follow-up disease assessments performed until study closure for a minimum of 5 years.

It is expected that the study will last approximately 60 months to reach the final analysis of the mPFS endpoint (approximately 36 months of enrollment plus 24 months of additional follow-up after the last patient is randomized). Patients will be followed for survival until death or the end of posttreatment follow-up (when 112 deaths occur, approximately 4 years from the date of the last patient randomized), whichever occurs first. The total study duration is approximately 7 years.

## **5. STUDY POPULATION**

Eligible patients with treatment-naïve advanced classical HL will be randomized to receive either A +AVD or ABVD.

### **5.1 Inclusion Criteria**

Each patient must meet all of the following inclusion criteria to be randomized to treatment:

1. Male or female patients 18 years or older.

**Brentuximab vedotin (ADCETRIS®)**

**Clinical Study Protocol C25003 Amendment 7, EudraCT: 2011-005450-60**

2. Treatment-naïve, HL patients with Ann Arbor Stage III or IV disease (refer to Section 15.1).
3. Patients must have histologically confirmed classical HL according to the current World Health Organisation Classification (nodular sclerosis, mixed cellularity, lymphocyte rich, lymphocyte depleted, or classical Hodgkin lymphoma, NOS [not otherwise specified]).
4. ECOG performance status  $\leq 2$  (refer to Section 15.2).
5. Patients must have bidimensional measurable disease as documented by radiographic technique (spiral CT preferred) per the International Working Group Revised Criteria for Response Assessment for Malignant Lymphoma (Cheson 2007).
6. Female patients who:
  - Are postmenopausal for at least 1 year before the screening visit, OR
  - Are surgically sterile, OR
  - If they are of childbearing potential, agree to practice 2 effective methods of contraception, at the same time, from the time of signing the informed consent through 6 months after the last dose of study drug, or
  - Agree to practice true abstinence, when this is in line with the preferred and usual lifestyle of the subject. (Periodic abstinence [eg, calendar, ovulation, symptothermal, postovulation methods] and withdrawal are not acceptable methods of contraception.)

Male patients, even if surgically sterilized (ie, status postvasectomy), who:

- Agree to practice effective barrier contraception during the entire study treatment period and through 6 months after the last dose of study drug, OR
- Agree to practice true abstinence, when this is in line with the preferred and usual lifestyle of the subject. (Periodic abstinence [eg, calendar, ovulation, symptothermal, postovulation methods for the female partner] and withdrawal are not acceptable methods of contraception.)

## **Brentuximab vedotin (ADCETRIS®)**

### **Clinical Study Protocol C25003 Amendment 7, EudraCT: 2011-005450-60**

7. Voluntary written consent must be given before performance of any study-related procedure not part of standard medical care, with the understanding that consent may be withdrawn by the patient at any time without prejudice to future medical care.
8. Suitable venous access for the study-required blood sampling, including PK sampling.
9. Clinical laboratory values as specified below within 7 days before the first dose of study drug:
  - Absolute neutrophil count  $\geq 1,500/\mu\text{L}$  unless there is known HL marrow involvement
  - Platelet count  $\geq 75,000/\mu\text{L}$  unless there is known HL marrow involvement
  - Total bilirubin must be  $< 1.5 \times$  the upper limit of normal (ULN) unless the elevation is known to be due to Gilbert syndrome.
  - ALT or AST must be  $< 3 \times$  the upper limit of the normal range. AST and ALT may be elevated up to 5 times the ULN if their elevation can be reasonably ascribed to the presence of HL in liver.
  - Serum creatinine must be  $< 2.0 \text{ mg/dL}$  and/or creatinine clearance or calculated creatinine clearance  $> 40 \text{ mL/minute}$  (refer to Section 15.3).
  - Hemoglobin must be  $\geq 8 \text{ g/dL}$ .

## **5.2 Exclusion Criteria**

Patients meeting any of the following exclusion criteria are not to be randomized to treatment.

1. Nodular lymphocyte predominant Hodgkin lymphoma
2. Female patients who are both lactating and breastfeeding or who have a positive serum pregnancy test during the screening period or a positive pregnancy test on Day 1 before first dose of study drug
3. Any serious medical or psychiatric illness that could, in the investigator's opinion, potentially interfere with the completion of treatment according to this protocol

**Brentuximab vedotin (ADCETRIS®)**

**Clinical Study Protocol C25003 Amendment 7, EudraCT: 2011-005450-60**

4. Known cerebral or meningeal disease (HL or any other etiology), including signs or symptoms of PML
5. Symptomatic neurologic disease compromising normal activities of daily living or requiring medications
6. Any sensory or motor peripheral neuropathy
7. Any active systemic viral, bacterial, or fungal infection requiring systemic antibiotics within 2 weeks prior to first study drug dose
8. Prior immunosuppressive chemotherapy, therapeutic radiation, or any immunotherapy (eg, immunoglobulin replacement, other monoclonal antibody therapies) within 12 weeks of first study drug dose
9. Known hypersensitivity to recombinant proteins, murine proteins, or to any excipient contained in the drug formulation of brentuximab vedotin or any component of ABVD
10. Known human immunodeficiency virus (HIV) positive
11. Known hepatitis B surface antigen-positive, or known or suspected active hepatitis C infection
12. Diagnosed or treated for another malignancy within 3 years before the first dose or previously diagnosed with another malignancy and have any evidence of residual disease. Patients with nonmelanoma skin cancer or carcinoma in situ of any type are not excluded if they have undergone complete resection.
13. Any of the following cardiovascular conditions or values within 6 months before the first dose of study drug:
  - A left-ventricular ejection fraction <50%
  - Myocardial infarction within 2 years of randomization
  - New York Heart Association (NYHA) Class III or IV heart failure (see Section 15.4).

## **Brentuximab vedotin (ADCETRIS®)**

### **Clinical Study Protocol C25003 Amendment 7, EudraCT: 2011-005450-60**

- Evidence of current uncontrolled cardiovascular conditions, including cardiac arrhythmias, congestive heart failure (CHF), angina, or electrocardiographic evidence of acute ischemia or active conduction system abnormalities

## **6. STUDY DRUG**

All protocol-specific criteria for administration of study drug must be met and documented prior to drug administration. Study drug will be administered only to eligible patients under the supervision of the investigator or identified subinvestigator(s). The components of ABVD used in this study will be supplied by the study site and will be billed to patients and/or their third-party payer (insurance) and/or the sponsor according to local regulations unless otherwise arranged between the study site and sponsor. Brentuximab vedotin will be supplied by the study sponsor.

Treatment for advanced HL has improved over the past 30 years with combination chemotherapy regimens. The current anthracycline-containing regimen of doxorubicin, bleomycin, vinblastine, and dacarbazine (ABVD) has been proven superior to alkylating agent regimens and results in a long-term cure rate of approximately 70% in patients with advanced disease. Although combination regimens have successfully been expanded to up to 8 chemotherapeutic agents in attempts to increase overall response, these additional agents have also produced increased toxicity. ABVD thus remains the standard of care in many regions.

However, of the four agents in ABVD, bleomycin is the agent most associated with unpredictable, life-threatening toxicity, and is thought to have the lowest single-agent activity. Standard practice in patients who develop BPT is to continue frontline therapy with AVD while omitting bleomycin. Retrospective analyses of CALGB 8251 and 8952 have shown no difference in response or relapse rates for patients who had bleomycin discontinued at any point in their frontline therapy. Due to the proven antitumor activity and manageable safety profile of brentuximab vedotin monotherapy, substituting brentuximab vedotin for bleomycin (A+AVD) is hypothesized to provide a PFS improvement over the standard ABVD regimen and eliminate the risk of BPT.

### **6.1 ABVD Administration**

**ABVD** consists of doxorubicin 25 mg/m^2, bleomycin 10 units/m^2, vinblastine 6 mg/m^2, and dacarbazine (DTIC) 375 mg/m^2.

- **A:** Doxorubicin: 25 mg/m^2 will be administered by IV infusion on Days 1 and 15 of each 28-day cycle
- **B:** Bleomycin: 10 units/m^2 will be administered by IV infusion on Days 1 and 15 of each 28-day cycle
- **V:** Vinblastine: 6 mg/m^2 will be administered by IV infusion on Days 1 and 15 of each 28-day cycle
- **D:** Dacarbazine (DTIC): 375 mg/m^2 will be administered by IV infusion on Days 1 and 15 of each 28-day cycle

ABVD is to be administered in the stated order, per institutional guidelines. If an investigator needs to choose a different order of administration of the study drugs, this must first be discussed with the CRO and/or the Millennium project clinician. The order of administration must not be changed for the 50-patient subset in each treatment arm from whom additional PK samples are to be obtained (see Section 7.4.19).

### **6.2 A+AVD Administration**

**A+AVD** consists of brentuximab vedotin (ADCETRIS®) 1.2 mg/kg plus doxorubicin 25 mg/m^2, vinblastine 6 mg/m^2, and dacarbazine (DTIC) 375 mg/m^2.

- **A:** Doxorubicin: 25 mg/m^2 will be administered by IV infusion on Days 1 and 15 of each 28-day cycle
- **V:** Vinblastine: 6 mg/m^2 will be administered by IV infusion on Days 1 and 15 of each 28-day cycle
- **D:** Dacarbazine (DTIC): 375 mg/m^2 will be administered by IV infusion on Days 1 and 15 of each 28-day cycle

AVD is to be administered first, in the stated order, per institutional guidelines. If an investigator needs to choose a different order of administration of the study drugs, this must

## **Brentuximab vedotin (ADCETRIS®)**

### **Clinical Study Protocol C25003 Amendment 7, EudraCT: 2011-005450-60**

first be discussed with the CRO and/or the Millennium project clinician. The order of administration must not be changed for the 50-patient subset in each treatment arm from whom additional PK samples are obtained (see Section 7.4.19).

Brentuximab vedotin is to be administered after AVD:

- **A:** brentuximab vedotin (ADCETRIS): 1.2 mg/kg will be administered by IV infusion over approximately 30 minutes on Days 1 and 15 of each 28-day cycle; the infusion is to start approximately 1 hour after the conclusion of the dacarbazine administration.

In the absence of infusion toxicities, the infusion rate for all patients must be calculated in order to achieve a 30-minute (approximate) brentuximab vedotin infusion period.

Brentuximab vedotin must not be administered as an IV push or bolus. It must be administered through a dedicated IV line and cannot be mixed with other medications.

The dose of brentuximab vedotin is 1.2 mg/kg. Dosing is based on patients' weight according to the institutional standard; however, doses will be adjusted for patients who experience a  $\geq 10\%$  change in weight from baseline. Actual weight will be used except for patients weighing greater than 100 kg; dose will be calculated based on 100 kg for these individuals. The dose will be rounded to the nearest whole number of milligrams.

Further brentuximab vedotin administration information can be found in the Pharmacy Binder.

No routine pre- or post-medications are required for A+AVD therapy.

## **6.3 Dose-Modification Guidelines**

### **6.3.1 Recommended Brentuximab Vedotin Dose Modifications for Treatment-Associated Toxicity**

Table 6-1 details the recommended brentuximab vedotin dose modifications to be enacted in the event of treatment-associated toxicity. Please also refer to Section 6.3.2 for criteria pertinent to ABVD and AVD dose modifications.

**Table 6-1 Recommended A+AVD Dose Modifications for Treatment-Associated Toxicity**

Toxicity	≤Grade 2		≥Grade 3	
Nonhematologic (excluding neuropathy)	Continue at same dose level.		Hold A+AVD dosing until toxicity has resolved to ≤Grade 2 or has returned to baseline. a	
Hematologic	Continue at same dose level.		For neutropenia, manage with growth factors (granulocyte colony stimulating factor [G-CSF] or granulocyte-macrophage colony stimulating factor [GM-CSF]) per institutional guidelines. For thrombocytopenia, consider platelet transfusion and/or proceed according to institutional guidelines. For anemia, manage per institutional guidelines.	
Peripheral neuropathy	Grade 1 Continue at same dose level.	Grade 2 Reduce dose to 0.9 mg/kg and resume treatment; if already at 0.9 mg/kg, continue dosing at that level.	Grade 3 Withhold brentuximab vedotin until toxicity is ≤Grade 2, then reduce dose to 0.9 mg/kg and resume treatment. If already at 0.9 mg/kg, consult with sponsor (AVD may be continued or held concurrently at physician's discretion.)	Grade 4 Discontinue brentuximab vedotin

a Patients who develop clinically insignificant Grade 3 or 4 electrolyte laboratory abnormalities may continue study treatment without interruption.

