#### **1.5 Potential Risks and Benefits**

As detailed in Section 1.3, brentuximab vedotin monotherapy has demonstrated therapeutic activity in CD30+ hematological malignancies.

Brentuximab vedotin treatment causes a peripheral neuropathy that is predominantly sensory. Cases of peripheral motor neuropathy have also been reported. Brentuximab vedotin-induced peripheral neuropathy is typically cumulative and generally reversible. In the SG035-0003 and SG035-0004 clinical studies, 54% of patients experienced neuropathy of any grade. Of these patients, 49% had complete resolution, 31% had partial improvement, and 20% had no improvement. Of the patients who reported neuropathy, 51% had residual neuropathy at the time of their last evaluation. Monitoring patients for symptoms of neuropathy, such as hypoesthesia, hyperesthesia, paresthesia, discomfort, a burning sensation, neuropathic pain or weakness is required. Patients experiencing new or worsening peripheral neuropathy may require brentuximab vedotin dose modifications, including a dose delay (see Table 6-1).

Infusion-related reactions, including anaphylaxis, have occurred with brentuximab vedotin. Monitoring of patients during infusion is required. If anaphylaxis occurs, the administration of brentuximab vedotin should be immediately and permanently discontinued and appropriate medical therapy administered. If an infusion-related reaction occurs, the infusion should be interrupted and appropriate medical management instituted. Patients who

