**Brentuximab vedotin (ADCETRIS®)**

**Clinical Study Protocol C25003 Amendment 7, EudraCT: 2011-005450-60**

have experienced a prior infusion-related reaction should be premedicated according to institutional guidelines for subsequent infusions. Premedication may include acetaminophen, an antihistamine and a corticosteroid.

Clinically significant laboratory abnormalities were to be reported as adverse events per the phase 2 study protocols. Central laboratory data were collected only predose for each treatment cycle. Few patients overall had postbaseline worsening to Grade 3 or higher in clinical laboratory values. The clinical laboratory parameters for which the most patients had new or worsening shifts to  $\geq$ Grade 3 were low neutrophils (11%), lymphocytes (11%), platelets (6%), leukocytes (5%), and high glucose (6%). Only 1 patient in the phase 2 studies had Grade 3 ALT and AST.

Any treatment that can decrease immune function may contribute to malignancy and infections; patients are to be monitored for these events during the treatment period and up to and including 30 days after the last dose of frontline therapy.

Complete blood counts should be monitored prior to each dose of brentuximab vedotin and more frequent monitoring should be considered for patients with Grade 3 or 4 neutropenia. Prolonged ( $\geq$ 1 week) severe neutropenia can occur. If Grade 3 or 4 neutropenia develops, manage by dose delays, reductions, or discontinuations (see [Table 6-1](#)).

Tumor lysis syndrome may occur. Patients with rapidly proliferating tumor and high tumor burden are at risk of tumor lysis syndrome and should be closely monitored. If tumor lysis syndrome occurs, take medically appropriate measures.

Stevens-Johnson syndrome has been reported with brentuximab vedotin. If Stevens-Johnson syndrome occurs, brentuximab vedotin must be discontinued and the appropriate medical therapy administered.

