### 6.3.2 Reference Therapy Dose Modifications

ABVD or AVD treatment should be modified or discontinued per applicable label/Summary of Product Characteristics (SmPC) instructions.

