### **Infusion-Related Reactions**

Infusion-related reactions may occur during the infusion of brentuximab vedotin. The infusion should be administered at a site properly equipped and staffed to manage an infusion-related reaction, including anaphylaxis should it occur. The patient should be observed for approximately 60 minutes following the first infusion of brentuximab vedotin. During this observation period, the IV line should remain open for at least 1 hour to allow administration of IV drugs if necessary. All supportive measures consistent with optimal patient care will be given throughout the study according to institution standards. Medications for infusion-related reactions, such as epinephrine and antihistamines should be available for immediate use.

Patients who experience a Grade 1 or 2 infusion-related reaction may receive subsequent brentuximab vedotin infusions with premedication consisting of acetaminophen (650 mg orally) and diphenhydramine (25-50 mg orally or 10-25 mg IV) or according to institutional standards, administered 30 to 60 minutes prior to each 30-minute brentuximab vedotin infusion.

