#### **7.7 Discontinuation of Treatment With Study Drug, and Patient Replacement**

Study drug must be permanently discontinued for patients meeting any of the following criteria:

- Completed 6 cycles of A+AVD or ABVD
- Investigator deems it is in the patient's best interest to discontinue

The primary reason for study treatment withdrawal must be documented.

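### The Table 6-1 hold rule for Grade 3 or higher nonhematologic toxicity is not reconciled with the Section 1.5 stops for anaphylaxis and Stevens-Johnson syndrome

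*Protocol*

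**What the plan says.** Protocol Section 6.3.1 presents Table 6-1 as the recommended brentuximab vedotin modifications for treatment-associated toxicity. The nonhematologic row leaves out neuropathy, which has its own row. At Grade 3 or higher it reads: "Hold A+AVD dosing until toxicity has resolved to ≤Grade 2 or has returned to baseline". One footnote qualifies it: "Patients who develop clinically insignificant Grade 3 or 4 electrolyte laboratory abnormalities may continue study treatment without interruption".

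Section 1.5, on risks and benefits, gives event-specific instructions. For anaphylaxis: "If anaphylaxis occurs, the administration of brentuximab vedotin should be immediately and permanently discontinued and appropriate medical therapy administered". For Stevens-Johnson syndrome: "If Stevens-Johnson syndrome occurs, brentuximab vedotin must be discontinued and the appropriate medical therapy administered". It also says that a patient with a prior infusion-related reaction, of whatever grade, should be premedicated for later infusions.

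Section 6.6 covers dosing after an infusion-related reaction in one sentence, which begins: "Patients who experience a Grade 1 or 2 infusion-related reaction may receive subsequent brentuximab vedotin infusions with premedication". It does not cover Grade 3 or higher.

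Section 7.7 has a mandatory list, introduced by "Study drug must be permanently discontinued for patients meeting any of the following criteria". Its two entries are completion of six cycles and the investigator's judgement of the patient's best interest. A separate, permissive list includes adverse events.

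**The concern.** Holding a regimen until a toxicity has improved to a stated grade is a different instruction from stopping one of its drugs for good. Severe anaphylaxis and Stevens-Johnson syndrome fall within the general row as worded, because neither the row nor its footnote takes them out. An investigator who looks up the action in the dose-modification table meets a hold with a release condition. One who looks in the risk section meets a stop.

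What is at stake is re-exposure after a life-threatening reaction, and uniform conduct across approximately 250 planned centers. A second gap is scope. The table row holds all of A+AVD, while Section 1.5 speaks of brentuximab vedotin alone, so it is also unclear what should happen to AVD.

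**Working it through.** No arithmetic applies. The check is whether the passages give one action per event, and whether any other operational section settles the difference.

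**Anaphylaxis, Grade 3 or higher**
- Section 1.5: immediate and permanent stop of brentuximab vedotin.
- Table 6-1: falls in the general row; hold A+AVD until Grade 2 or lower, or baseline.
- Sections 6.5 and 6.6: site readiness and the observation period only; no rule on stopping.
- Section 7.7: not named.

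**Stevens-Johnson syndrome, Grade 3 or higher**
- Section 1.5: brentuximab vedotin must be stopped. Unlike the anaphylaxis sentence, this one does not say that the stop is permanent.
- Table 6-1: general row, as above.
- Rest of Section 6: the event is not mentioned.
- Section 7.7: not named.

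**Other infusion-related reactions, Grade 3 or higher**
- Section 1.5: interrupt the infusion and manage; premedicate for later infusions, with no limit by grade.
- Section 6.6: further dosing addressed for Grades 1 and 2 only.
- Table 6-1: the general row applies by default.

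**Does another section settle it?** Section 6.3.2 does not. It says "ABVD or AVD treatment should be modified or discontinued per applicable label/Summary of Product Characteristics (SmPC) instructions", which covers the reference drugs and not brentuximab vedotin. Section 7.7 allows a stop on the investigator's judgement or for an adverse event, but that is discretion and does not state the Section 1.5 rule.

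**Does the protocol's layout suggest an omission?** Section 1.5 sends the reader to Table 6-1 for neuropathy and neutropenia, and to Section 6.6 for suspected PML. Section 6 then carries the matching instructions, including stops for Grade 4 neuropathy and confirmed PML. For anaphylaxis and Stevens-Johnson syndrome, Section 1.5 gives no cross-reference and Section 6 has no matching stop.

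**Section 7.7 against other sections.** Section 10.4 requires a patient who becomes pregnant to stop study drug permanently. That is a stop of study drug as such, and the mandatory list in Section 7.7 omits it.

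**The case against.** The best defence is that Section 1.5 is part of the protocol that investigators agree to follow, is worded as a directive, and is specific where the table row is general. A specific rule would ordinarily prevail. Table 6-1 is headed as recommended. Its nonhematologic cell never says that treatment resumes, whereas the neuropathy cells do. Section 7.7 also requires a stop whenever the investigator judges that best for the patient.

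Much of this stands. A reader might infer that sites would rechallenge patients after anaphylaxis. The documents do not show that: resumption is only implied, and the stop is written down elsewhere. What remains is that a reader of the table alone can miss the rule, and that nothing in the table or Section 6.6 points to it.

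Four further inferences should be resisted.
- PML and Grade 4 neuropathy are not contradictions. Both have explicit stops in Section 6. Those stops concern brentuximab vedotin only, so their absence from a study-drug list is not in itself an error. Table 8-1, footnote a, accepts that single agents may be dropped.
- Sections 1.5 and 6.6 do not disagree on premedication after Grade 1 or 2 reactions. The permission in Section 6.6 concerns further infusions, with premedication as part of it. The difference lies in the grades covered.
- The table's rule does not reach every nonhematologic toxicity, because neuropathy is excluded.
- The rate in Section 1.3 of about 10% for infusion-related reactions cannot size the problem. It covers all grades and comes from phase 2 monotherapy at another dose and schedule, in relapsed or refractory disease. The same section reports the acute infusion reactions in Study SG035-0002 as below Grade 2. It lists no infusion reaction, anaphylaxis or Stevens-Johnson syndrome among the Grade 3 or higher events in the 26 patients given brentuximab vedotin with AVD.

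**Conclusion.** The conflict is real and lies in the text. For anaphylaxis and Stevens-Johnson syndrome at Grade 3 or higher, Table 6-1 and Section 1.5 give different actions, and neither Section 6 nor Section 7.7 resolves the difference. For other Grade 3 or higher infusion-related reactions, Section 6.6 is silent and the remaining passages do not yield one action.

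The number of patients affected cannot be derived from the documents, and the events may be few. The finding does not rest on frequency. It rests on two instructions for the same life-threatening event in one protocol. It assumes only that the general row is read as worded, so that it includes any nonhematologic event that it does not exclude.

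A reader might go further and conclude that one of the two rules is clinically wrong. The documents do not support that, and no view is taken here on which should govern.

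**What to change.** Reconcile Section 1.5, Table 6-1 and Section 6.6 so that anaphylaxis, Stevens-Johnson syndrome and Grade 3 or higher infusion-related reactions each have one stated action. Either take these events out of the general nonhematologic row or add a cross-reference from that row to the place where the action stands. For each event, state whether the action applies to brentuximab vedotin alone or to the whole regimen, and what then happens to AVD.

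Align Section 7.7 with the stops stated elsewhere, including the study-drug stop for pregnancy in Section 10.4, and make clear whether its list covers study drug as a whole or single agents as well.

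The sponsor's safety team decides the clinical action. The cost is protocol wording and a memo to sites; no procedures or patients are added.
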